9.6.4. Antiemetic Therapy

The use of antiemetic agents is permitted during this study.

9.6.5. Analgesic Agents

The use of analgesic agents is permitted at the discretion of the investigator.

9.6.6. Bisphosphonates and RANK-L Targeted Agents

Patients with bone metastases present on baseline imaging are allowed treatment with bisphosphonates or receptor activator of nuclear factor kappa-B ligand (RANK-L) targeted agents (for example, denosumab), per respective approved labels. Initiation of treatment with bone-modifying agents must begin at least 7 days prior to enrollment. Patients receiving bisphosphonates or RANK-L targeted agents should not switch treatments (for example, replace

a bisphosphonate with denosumab) while on study treatment. However, exceptional cases without evidence of PD may be considered in consultation with the Lilly CRP. These exceptional cases will not incur a protocol deviation.

9.6.7. Therapy for Febrile Neutropenia

Patients experiencing febrile neutropenia, especially with diarrhea or dyspnea, should be managed in a hospital setting according to standard procedures, with the urgent initiation of intravenous antibiotic therapy. Events that require a patient to be hospitalized are considered SAEs (see Section 10.2.1.1).

9.7. Treatment Compliance

Pembrolizumab and necitumumab will be administered I.V. at the investigational site, under the direction of the investigator. As a result, a patient's compliance with study drug administration is ensured. Patients should attend scheduled clinic visits and must comply with study criteria under their control.

Patients who are significantly noncompliant will be discontinued from the study. A patient will be considered significantly noncompliant if he or she delays therapy for more than 6 weeks following Day 1 of the most recent cycle during the study.

The study medication will be administered only at the investigational sites by the authorized study personnel. As a result, treatment compliance is ensured.

Potential discontinuation of a patient due to study drug noncompliance will be discussed between the investigator and the Lilly CRP before any determination is made to discontinue the patient.

10. Efficacy, Safety Evaluations, Sample Collection and Testing, and Appropriateness of Measurements

Written informed consent must be obtained prior to any study-specific pretreatment evaluations.

Study procedures related to efficacy, safety, and sample collection and testing assessments and their timing are described in the sections below and shown in the Study Schedule ([Attachment 1](#)).

10.1. Efficacy Measures

10.1.1. Efficacy Assessments at Baseline and during Study Treatment

Within 21 days before the first dose of study drug, baseline tumor measurements will be performed on each patient. Throughout the study, patients will be evaluated for response according to RECIST 1.1 (Eisenhauer et al. 2009). For the purpose of patient management, RECIST 1.1 with adaptation (irRECIST) will be used to assess tumor response (see Section [10.1.5.1](#)).

A contrast computed tomography (CT) scan or magnetic resonance imaging (MRI) of the brain will be performed at pretreatment only, and thereafter approximately every 6 weeks \pm 5 days, if a patient had brain metastases at study entry or if clinically indicated.

Computed tomography, including spiral CT, scans and MRI are the preferred methods of measurement.

The method of assessment used at baseline must be used consistently during the course of each patient's evaluation during the study.

Imaging studies required to investigate known disease should be repeated every 6 weeks (\pm 5 days) following the first dose of study therapy, regardless of any treatment delays, until radiographic documentation of PD as defined by RECIST 1.1, with adaptation described below in more detail (irRECIST; see Section [10.1.5.1](#)).

CT of the chest and CT or MRI of the abdomen and pelvis is required at each time point; CT/MRI of the brain must be performed if baseline assessment identified any lesion in this area (or if clinically indicated).

Responses (CR or PR) must be confirmed at least 28 days from the first evidence of response. Thereafter, a responding patient will be followed approximately every 6 weeks (\pm 5 days) until objective progression is observed.

For patients continuing treatment after study completion (continued access period), efficacy assessments (frequency and type of assessments) will be at the discretion of the investigator, based on the standard of care.

Response assessments during the ongoing trial (and related treatment decisions) will be performed by the treating investigator at the site in cooperation with the local radiologist(s).

10.1.2. Efficacy Assessments during the Study Period Postdiscontinuation Follow-Up

Postdiscontinuation follow-up during the study period will be conducted as described in the Study Schedule ([Attachment 1](#)).

For those patients who discontinue study treatment without objectively measured PD, the investigative sites will continue to monitor patients and periodically evaluate tumor response at the same frequency and by the same method used at baseline and throughout the study until the patient has objective disease progression, starts a new anticancer therapy, or until study completion, whichever occurs first. After the patient has objective disease progression (as determined using methodology described below) or starts a new anticancer therapy, radiologic tests are no longer required and the patient will be followed up approximately every 3 months [± 7 days] until the patient's death or overall study completion, whichever comes first.

Response (CR or PR) should be confirmed before the initiation of additional anticancer therapy. However, initiation of new therapy should not be delayed solely to confirm response.

After patients have discontinued study treatment, they may receive additional anticancer therapy at the discretion of the investigator. These postdiscontinuation therapies must be documented on the CRF.

10.1.3. Primary Efficacy Measure (Part B only)

10.1.3.1. Tumor Imaging and RECIST Assessment

Local site study team reading (investigator assessment with site radiology reading) based on RECIST 1.1 will be used to determine patient eligibility. Tumor imaging should be performed by CT (preferred). MRI should only be used when CT is contraindicated or for imaging in the brain, but the same imaging technique should be used in a patient throughout the trial.

Imaging should include the chest, abdomen, and pelvis.

10.1.3.1.1. Initial Tumor Imaging

Initial tumor imaging at screening must be performed within 21 days prior to the date of the first dose of trial treatment. The site study team must review screening images to confirm the patient has measurable disease per RECIST 1.1. Scans performed as part of routine clinical management are acceptable for use as initial tumor imaging if they are of diagnostic quality and performed within 21 days prior to the date of first dose.

10.1.3.1.2. On Study Tumor Imaging

The first on-study imaging assessment should be performed at 6 weeks (± 5 days) from the date of first dose of trial treatment. Subsequent tumor imaging should be performed every 6 weeks (± 5 days) or more frequently only if clinically indicated. Imaging should not be delayed for delays in any of the study drug dosing. Continue to perform imaging until whichever of the following occurs first:

- Initial site-assessed disease progression is confirmed (Section [10.1.5.1](#))
- The start of new anti-cancer treatment
- Withdrawal of consent
- Death
- The end of the study

10.1.3.2. Tumor Response Assessment

The primary efficacy measure is ORR as defined by RECIST 1.1 (Eisenhauer et al. 2009) provided in [Attachment 5](#). A responder is defined as any patient who exhibits a confirmed CR or PR.

Best response is determined from the sequence of responses assessed.

Per RECIST 1.1, partial or complete response should be confirmed by a repeat tumor imaging assessment. A second assessment must be performed ≥ 28 days after the first evidence of response or at the next scheduled scan (that is, 6 weeks later), whichever is clinically indicated. Two objective status determinations of CR before progression are required for a best response of CR. Two determinations of PR or better before progression, but not qualifying for a CR, are required for a best response of PR. Best response of SD is defined as disease that does not meet the criteria for CR, PR, or PD and has been evaluated at least 1 time, at least 6 weeks after the start of study treatment.

Best response will be derived to encompass all tumor assessments from baseline until the earliest of objective progression or start of new anticancer therapy. Any responses observed after objective progression or the start of new anticancer therapy are excluded from the determination of best response.

The date of first documented objective disease progression must be recorded on the CRF even if it occurs after the patient has started a new therapy.

10.1.4. Secondary Efficacy Measures

The secondary efficacy measures, including DCR, DOR, PFS, and OS, will be collected at the times shown in the Study Schedule ([Attachment 1](#)).

10.1.5. Exploratory Efficacy Measures

10.1.5.1. Adapted RECIST 1.1 (irRECIST)

RECIST 1.1 will be adapted to account for the unique tumor response characteristics seen with treatment of pembrolizumab. Immunotherapeutic agents such as pembrolizumab may produce antitumor effects by potentiating endogenous cancer-specific immune responses. The response patterns seen with such an approach may extend beyond the typical time course of responses seen with cytotoxic agents, and can manifest a clinical response after an initial increase in tumor burden or even the appearance of new lesions. Standard RECIST 1.1 assessment may not

provide an accurate response assessment of immunotherapeutic agents such as pembrolizumab. Therefore, RECIST 1.1 will be used with the following adaptations:

- If radiologic imaging verifies initial PD, tumor assessment should be repeated ≥ 4 weeks later in order to confirm PD with the option of continuing treatment per [Table JFCQ.10.1](#) below while awaiting radiologic confirmation of progression.
- If repeat imaging shows $< 20\%$ tumor burden compared to nadir, stable or improved previous new lesion (if identified as cause for initial PD), and stable/improved non-target disease (if identified as cause for initial PD), treatment may be continued/resumed.
- If repeat imaging confirms PD due to any of the scenarios list below, patients will be discontinued from study therapy and proposed best alternative available.

In determining whether or not the tumor burden has increased or decreased, site study team should consider all target lesions as well as non-target lesions.

Scenarios where PD is confirmed at repeat imaging:

- Tumor burden remains $\geq 20\%$ and at least 5-mm absolute increase compared to nadir
- Non-target disease resulting in initial PD is worse (qualitative)
- New lesion resulting in initial PD is worse (qualitative)
- Additional new lesion(s) since last evaluation

In patients who have initial evidence of radiological PD, it is at the discretion of the treating physician whether to continue a patient on study treatment until repeat imaging is obtained. This clinical judgment decision should be based on the patient's overall clinical condition, including performance status, clinical symptoms, and laboratory data. Patients may receive pembrolizumab and necitumumab treatment while waiting for confirmation of PD if they are clinically stable as defined by the following criteria:

- Absence of signs and symptoms (including worsening of laboratory values) indicating disease progression
- No decline in ECOG PS, apart from change from PS0 to PS1
- Absence of rapid progression of disease
- Absence of progressive tumor at critical anatomical sites (for example, cord compression) requiring urgent alternative medical intervention

When feasible, patients should not be discontinued from study therapy until progression is confirmed. This allowance to continue treatment despite initial radiologic progression takes into account the observation that some patients can have a transient tumor flare in the first few months after the start of immunotherapy, but with subsequent disease response. Patients that are deemed clinically worsening/deteriorating are not required to have repeat imaging for confirmation of progressive disease (see [Table JFCQ.10.1](#)).

Table JFCQ.10.1. General Guidance for Decision Making on Repeated Radiologic Assessment in Patients with Initial PD based on Clinical Status

	Clinically Stable		Clinically Worsening/Deterioration	
	Imaging	Treatment	Imaging	Treatment
First radiologic evidence of PD by RECIST 1.1	Repeat imaging at ≥ 4 weeks to confirm PD	May continue study treatment at the local site investigator's discretion while awaiting confirmatory scan by irRECIST	Repeat imaging at ≥ 4 weeks to confirm PD if possible	Discontinue study treatment
Repeat scan confirms PD by irRECIST at the local site	No additional imaging required	Discontinue study treatment (exception is possible upon consultation with sponsor)	No additional imaging required	N/A
Repeat scan shows SD, PR, or CR (compared to scan showing first radiologic evidence of PD) by irRECIST at the local site	Continue regularly scheduled imaging assessments every 6 weeks (± 5 days)	Continue study treatment at the local site investigator's discretion	Continue regularly scheduled imaging assessments every 6 weeks (± 5 days)	May restart study treatment if condition has improved and/or clinically stable per investigator's discretion

Abbreviations: CR = complete response; N/A = not applicable; PD = progressive disease; PR = partial response; SD = stable disease.

NOTE:

- If a patient has confirmed radiographic progression (i.e., 2 scans at least 4 weeks apart demonstrating progressive disease) per irRECIST, but the patient is achieving a clinically meaningful benefit, and there is no further increase in the tumor burden at the confirmatory tumor imaging, an exception to continue treatment may be considered following consultation with the Sponsor.
- Any patient deemed clinically unstable should be discontinued from trial treatment at first radiologic evidence of PD and is not required to have repeat imaging for PD confirmation.
- In patients who discontinue study therapy without documented disease progression, every effort should be made to continue monitoring their disease status by tumor imaging using the same imaging schedule used while on treatment every 6 weeks (± 5 days), until (1) the start of new anti-cancer treatment, (2) disease progression, (3) death, or (4) the end of the study, whichever occurs first.

The following exploratory efficacy measures will be collected at the times shown in the Study Schedule ([Attachment 1](#)). Confirmation by 2 consecutive observations at least 4 weeks apart is required for CR, PR, and PD for both assessments to assign best response for each patient:

- immune-related CR (irCR): disappearance of all lesions
- immune-related PR (irPR): $\geq 30\%$ decrease of total tumor burden from baseline
- immune-related PD (irPD): $\geq 20\%$ increase of total tumor burden from the nadir
- immune-related SD (irSD): fail to meet criteria for irCR or irPR in the absence of irPD

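### After burden-driven progression, a plateaued tumor is confirmed PD under the text of Protocol Section 10.1.5.1 but reads as stable under the third row of Table JFCQ.10.1

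*Protocol*

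**What the plan says.** Protocol Section 10.1.5.1 gives the rule for the repeat scan in several places.

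- **Text, PD confirmed.** For tumor burden, PD is confirmed if the sum remains 20% or more above nadir "and at least 5-mm absolute increase compared to nadir". In that case "patients will be discontinued from study therapy and proposed best alternative available".
- **Text, PD not confirmed.** If burden is less than 20% above nadir, and any new or non-target lesion that caused the first PD is stable or improved, "treatment may be continued/resumed".
- **Definitions.** irPD is a rise of at least 20% from nadir. irSD requires that irPD is absent.
- **Table JFCQ.10.1, row 2 (repeat scan confirms PD).** A clinically stable patient stops treatment, with an exception possible after sponsor consultation. For a clinically worsening patient the treatment cell is not applicable.
- **NOTE under the table.** For confirmed progression with clinically meaningful benefit and no further growth on the confirmatory scan, "an exception to continue treatment may be considered following consultation with the Sponsor".
- **Table JFCQ.10.1, row 3.** The row is labelled "Repeat scan shows SD, PR, or CR (compared to scan showing first radiologic evidence of PD) by irRECIST at the local site". A clinically stable patient continues at the investigator's discretion. For a patient who had been worsening, the cell reads "May restart study treatment if condition has improved and/or clinically stable", again at the investigator's discretion. Neither cell mentions the sponsor.

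Protocol Section 10.1.1 uses irRECIST for patient management. Section 7.3.2 requires discontinuation for PD confirmed by irRECIST and cites both Section 10.1.5.1 and this table. SAP Section 5.5.6.5 applies irRECIST as the protocol sets it out and names no reference scan of its own for confirming PD.

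**The concern.** The text, the definitions and (through them) row 2 measure tumor burden from nadir. Row 3 prints the first-PD scan as its comparator. A tumor that grew enough to be PD and then stopped growing is still well above nadir but unchanged from the first-PD scan. The same patient can therefore be placed in row 2 or in row 3.

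The two rows have different consequences. Under row 2 and the NOTE, treatment beyond confirmed PD is an exception that involves the sponsor, and the NOTE also asks for clinically meaningful benefit. A site following row 3 as printed applies neither condition. It may also restart drug in a patient who was taken off for clinical deterioration and whose repeat scan is flat. Identical scans could then lead to different decisions at different sites, and some patients with confirmed PD could stay on the combination instead of moving to another therapy.

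The point concerns only PD driven by tumor burden. For PD caused by new or non-target lesions, the text uses a qualitative judgment of worse versus stable or improved.

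**Working it through.** The plan states no figure on this point, so there is none to reproduce. The check applies each printed rule to the same lesion sums. The sums are illustrative; the limits come from Protocol Section 10.1.5.1.

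**Rule A (text and irPD definition).** Change = (repeat − nadir) / nadir. PD is confirmed if the change is at least 20% and repeat − nadir is at least 5 mm.

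**Rule B (row 3 comparator).** Change = (repeat − first-PD sum) / first-PD sum. The protocol prints no limits for this comparison, but a change of 0% is stable under any limit.

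**Plateau, nadir 80 mm, first PD 100 mm, repeat 100 mm**

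- Rule A: (100 − 80) / 80 = +25%, and 100 − 80 = 20 mm. Both limits are met, so PD is confirmed.
- Rule B: (100 − 100) / 100 = 0%, so SD.

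**Other sums.** Where Rule B needs limits, the rows below assume the usual ones (+20% and 5 mm for PD, −30% for PR) applied to the first-PD scan.

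| Nadir → first PD → repeat (mm) | Versus nadir | Rule A | Versus first-PD scan | Rule B |
|---|---|---|---|---|
| 50 → 60 → 60 | +20%, +10 mm | confirmed PD | 0% | SD |
| 50 → 62 → 62 | +24%, +12 mm | confirmed PD | 0% | SD |
| 50 → 65 → 65 | +30%, +15 mm | confirmed PD | 0% | SD |
| 50 → 62 → 74 | +48%, +24 mm | confirmed PD | +19.4% | SD (assumed limits) |
| 50 → 62 → 59 | +18%, +9 mm | not confirmed | −4.8% | SD (assumed limits) |

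The plateau result is general. If the first PD was at least 20% and 5 mm above nadir, an unchanged repeat sum is too, and its change from the first-PD scan is always 0%. The two rules agree in the last row, where burden falls back to less than 20% above nadir.

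**Reach into the endpoints**

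- Primary ORR: Protocol Section 10.1.3.2 and SAP Section 5.5.5 exclude responses after objective progression, so it does not move.
- RECIST 1.1 PFS: the event is the first objective PD, so it does not move.
- irPFS and irDOR: SAP Section 5.5.6.5 dates irPD at the first PD if it is confirmed, and at a later non-consecutive PD if it is not. The date changes only if a site records SD on the row 3 comparator, contrary to the irSD definition. No delay in weeks is calculated, because Protocol Section 10.1.3.1.2 allows scans more often than every 6 weeks.
- irDCR: this changes only under the same condition, and only if the patient had no earlier SD or better. One patient is 1/54 = 1.85 percentage points with 54 evaluable patients. With 6 Part A patients at the recommended dose added (54 + 6 = 60), one patient is 1/60 = 1.67 points.

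**The case against.** The strongest reply is that row 3 also says the response is judged by irRECIST. By the protocol's own definition irSD cannot coexist with irPD, and irPD is measured from nadir. On that reading the 80/100/100 mm plateau is irPD and belongs in row 2 only. The comparator in brackets would then merely say which scan precedes the repeat. It could not replace the reference for irPR, which is baseline, or for irCR, which needs none. In addition, the NOTE already covers confirmed PD without further growth, the table is titled general guidance, and SAP Section 5.4 lists treatment continued after PD as an important protocol violation.

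Part of this stands. Nadir was very probably intended, and no limits are printed for a comparison with the first-PD scan, so the 50 → 62 → 74 mm example rests on an assumption. The endpoint effect is exploratory and conditional, and 1/n per patient is a unit of change, not an estimated effect.

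It does not remove the conflict. The row states its comparator expressly, and a site using the table for a treatment decision can reasonably follow it. The NOTE makes the contradiction plainer: it treats a tumor that has stopped growing as confirmed PD needing sponsor consultation, while row 3 as printed hands the same tumor to the investigator. The guidance title carries little weight when Section 7.3.2 cites the table in a discontinuation criterion. The SAP violation item does not say whether it means first or confirmed PD, so a site following row 3 might be counted as a violator for doing what the table allows.

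**Conclusion.** The concern holds. For PD driven by tumor burden, every exact plateau at the repeat scan is confirmed PD against nadir and stable against the comparator printed in row 3. The consequence is discontinuation with a sponsor-consulted exception under one rule, and continuation or restart at the investigator's sole discretion under the other. The plateau result assumes only that a burden-driven first PD meets the same 20% and 5-mm limits, as the confirmation rule implies by asking whether the burden remains there.

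The main effect is on treatment decisions and their consistency across sites. The effect on exploratory irRECIST endpoints is conditional on how sites record the scan; for irDCR it is 1.7 to 1.9 percentage points per patient. That range assumes an evaluable-patient denominator of 54 to 60, the upper end taking all 6 Cohort 2 patients as evaluable at the recommended dose. The number of patients who would plateau in this way cannot be derived from the documents. Primary ORR and RECIST 1.1 PFS are not affected. This should be corrected, but it does not threaten the primary analysis.

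**What to change.** In row 3 of Table JFCQ.10.1, replace the bracketed comparator with: *does not meet the confirmed-PD scenarios of Section 10.1.5.1 (tumor burden judged against nadir; new and non-target lesions judged as stable/improved versus worse)*.

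The 80/100/100 mm plateau then falls in row 2 only, and continuing needs the sponsor-consulted exception. A repeat such as 50 → 62 → 59 mm, at +18% from nadir and with no other sign of PD, stays in row 3 at the investigator's discretion.

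The cost is one phrase in one protocol table. No new data are needed. The SAP needs no change, because it relies on the protocol's irRECIST, which already measures irPD from nadir and irPR from baseline.

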5.5.6.5. Exploratory Outcome and Methodology Based on irRECIST

The irORR, irDCR, irDOR, and irPFS assessment based on adapted RECIST 1.1 (irRECIST) will be used for exploratory analysis to account for the unique tumor response characteristics

seen with treatment of pembrolizumab. irRECIST will be applied as detailed in the study protocol, and the resulting data will be included in the clinical database.

Objective response rate (irORR) is defined as the proportion of evaluable patients achieving a best overall response of PR or CR per irRECIST. Particularly, the best overall response by irRECIST is closely related to confirmed response by RECIST. IrORR further captures responses after unconfirmed PD and it does not require confirmation. In addition, patients’ responses after start of new anticancer therapy are excluded from the determination of best response. For example:

- If the best response by RECIST is CR, then the best response by irRECIST is CR.
- If the best response by RECIST is PR, SD, or PD, the best response by irRECIST is the best response over the initial assessment (prior to PD by RECIST) and the confirmation stage.

Overall, the best response by irRECIST should be the same or better than the best response by RECIST criteria.

[figure not shown]
IrPFS: The date from the treatment started date to the time of PD assessed by irRECIST or death from any cause, whichever comes first.

- If the initial PD is confirmed, then the date of immune-related (ir)PD is the initial PD date by RECIST.
- If the initial PD is unconfirmed, then the date of irPD is the date of second non-consecutive PD.

Duration of response by irRECIST: The duration of response is defined from the date of first documented irCR or irPR (responder) to the date of irPD or the date of death due to any cause, whichever is earlier.

[figure not shown]
Graphic Example:

Scenario 1: The initial PD is confirmed at the next scan (consecutive PD). The efficacy variables by irRECIST and RECIST are the same.

Scenario 2: The initial PD is not confirmed at the next scan (non-consecutive PD). The efficacy variables by irRECIST and RECIST may be different.

PFS by irRECIST

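### Protocol 10.1.5.1 defines irRECIST progression in two ways that disagree on new lesions and on the 5-mm minimum, leaving best response for irDCR ambiguous

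*Protocol*

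**What the plan says.** Protocol 10.1.5.1 describes progression under irRECIST twice.

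- **Repeat-imaging list.** Under "Scenarios where PD is confirmed at repeat imaging" there are four routes, any one of which is enough: tumor burden still at least 20% and at least 5 mm above nadir; non-target disease that caused the initial PD and is now worse; a new lesion that caused the initial PD and is now worse; and "Additional new lesion(s) since last evaluation". The last three are qualitative or carry no size threshold. Table JFCQ.10.1 treats this outcome as PD by irRECIST.
- **Best-response definitions.** At the end of the same section, the categories used to assign best response give irPD one route only, a 20% or greater "increase of total tumor burden from the nadir". irPR is a 30% or greater "decrease of total tumor burden from baseline". irSD is the remainder: "fail to meet criteria for irCR or irPR in the absence of irPD".

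On what burden covers, the section says that the "site study team should consider all target lesions as well as non-target lesions". New lesions are not named there, and total tumor burden is not defined in the readable text.

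SAP 5.5.6.5 refers to the protocol for how irRECIST is applied. For irPFS it adds a dating rule: "If the initial PD is confirmed, then the date of immune-related (ir)PD is the initial PD date by RECIST". Its Scenario 1 says that once the initial PD is confirmed, irRECIST and RECIST give the same efficacy variables.

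**The concern.** The two rules can give different answers for the same scans. The best-response definitions have no new-lesion route and no 5-mm minimum. Because irSD is the default category, a patient whose progression by new lesions has been confirmed can still be recorded as stable and counted as disease control.

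An irDCR above the RECIST DCR is meant to show patients whose initial PD was not borne out. Here part of the gap could come from the wording instead. Assessment is by the investigator at the site (Protocol 10.1.1) and the irRECIST results go into the clinical database (SAP 5.5.6.5), so sites could code identical scans differently.

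**Working it through.** The plan states no figure that depends on this definition, so there is none to reproduce. The check applies both rules to hypothetical lesion sums.

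**Formulas.** Let B be the burden at the repeat scan.
- Change from nadir = (B − nadir) / nadir; irPD if this is +20% or more.
- Change from baseline = (B − baseline) / baseline; irPR if this is −30% or lower and irPD is not met.
- Otherwise irSD (irCR does not arise here).

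The documents do not say whether new lesions enter B, so both readings are run. In rows 1 to 5 the initial PD came from a new lesion, and the repeat scan shows that lesion worse or another one added.

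| Row | Baseline / nadir / current sum (mm) | New lesion (mm) | Best-response definitions, new lesion left out | Best-response definitions, new lesion added | Repeat-imaging list |
|---|---|---|---|---|---|
| 1 | 60 / 60 / 60 | 10 | 0%: irSD | (70 − 60)/60 = +16.7%: irSD | PD confirmed |
| 2 | 60 / 60 / 60 | 12 | 0%: irSD | (72 − 60)/60 = +20.0%: irPD | PD confirmed |
| 3 | 60 / 50 / 50 | 8 | 0% from nadir, −16.7% from baseline: irSD | (58 − 50)/50 = +16.0%: irSD | PD confirmed |
| 4 | 60 / 36 / 36 | 6 | 0% from nadir, −40.0% from baseline: irPR | (42 − 36)/36 = +16.7%, (42 − 60)/60 = −30.0%: irPR | PD confirmed |
| 5 | 60 / 36 / 36 | 8 | 0% from nadir, −40.0% from baseline: irPR | (44 − 36)/36 = +22.2%: irPD | PD confirmed |
| 6 | 30 / 20 / 24 | none | (24 − 20)/20 = +20.0%: irPD | same | Burden route not met: 4 mm is below 5 mm |

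**Reading the table.**
1. If new lesions are outside the burden, the rules conflict for a new lesion of any size (rows 1 to 5).
2. If they are inside, and the other lesions are at their nadir, the conflict remains for new lesions totalling less than 20% of the nadir sum: 0.20 × 60 = 12 mm in rows 1 and 2.
3. Row 4 shows that the conflicting category can be irPR, so irORR is not immune.
4. Row 6 is a conflict in the other direction.

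**Which endpoints.** SAP 5.5.6.5 takes best irRECIST response over the assessments before RECIST PD and the confirmation stage. A patient who already had qualifying SD counts as disease control under either rule. The difference arises for patients whose PD comes at the first scan, because for them the confirmation-stage category decides. SAP 5.5.6.5 names irDCR without spelling it out; I take it as DCR with the ir categories. The same patient has an irPFS event at the initial PD date under the SAP dating rule, and so could carry an irPFS event together with a best response of irSD.

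**Size.** With 54 evaluable patients, each reclassified patient moves irDCR by 1/54 = 1.85 percentage points. The documents give neither the proportion with PD at first scan nor the share confirmed by new lesions alone, so this cannot be turned into an expected shift.

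**The case against.** **The SAP already settles it.** The best-response definitions are not an event-dating rule. SAP 5.5.6.5 dates irPD at the initial RECIST PD once that is confirmed, and the only list of confirming findings is the four-route one. This stands for irPFS, and largely for irDOR. It stands only in part for irDCR. Scenario 1 points to the right answer, but it is a worked example and gives no components of irPD. The SAP otherwise sends the reader back to the protocol. Its general remark that the irRECIST response should be no worse than the RECIST one would also accept irSD.

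**Burden may include new lesions.** The sentence on burden does not exclude them, and the RECIST attachment is redacted, so nothing can be drawn from its absence. This narrows the conflict but does not remove it, as rows 1, 3 and 4 show. The non-target route is weaker than the new-lesion route, since non-target lesions are expressly considered in the burden; still, a qualitative worsening cannot be tested against a 20% threshold.

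**The endpoints are exploratory.** No test or decision rule rests on them, and Protocol 8.2 calls the outcome hypothesis generating only. This stands and sets the severity.

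**A stronger reading is tempting.** A reader might infer that confirmed new-lesion progressors stay event-free, so that irPFS and irDOR are materially inflated. The documents do not support that. The SAP dating rule makes these patients events at the initial PD. Deaths are events under either definition. Protocol 10.1.3.1.2 and Table JFCQ.10.1 end required imaging once PD is confirmed, so a later burden-based progression would generally not be observed.

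**Conclusion.** The contradiction is real and no readable text resolves it. Taken literally, the best-response definitions code a confirmed new-lesion progressor as irSD, or as irPR after 30% shrinkage, against the repeat-imaging list and the SAP's own Scenario 1. They also call a rise of at least 20% but under 5 mm irPD, which the list's burden route does not.

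The severity is minor. The effect is on exploratory best response: mainly irDCR, possibly irORR. irPFS and irDOR are largely protected. Primary ORR and secondary DCR, DOR and PFS use RECIST 1.1 and do not change. The only firm size is 1.85 points of irDCR per reclassified patient, assuming 54 evaluable; any overall range would rest on shares the documents do not give. The conclusion about new lesions does not depend on whether they count in the burden; only its extent does.

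**What to change.** - **Protocol 10.1.5.1.** For the exploratory endpoint analysis, align the irPD definition used for best response with the confirmed-PD components listed earlier in the section, including the 5-mm minimum, and let irSD follow from it. State whether new lesions enter total tumor burden.
- **SAP 5.5.6.5.** State that this one definition is used for irDCR, irORR, irPFS and irDOR, consistent with Scenario 1.
- **Protocol 7.3.2.** Discontinuation of study therapy also refers to PD confirmed by irRECIST. The two parts of 10.1.5.1 must be reconciled for that use as well. Which clinical rule should apply there is for the sponsor to settle, not for this review.

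The cost is wording in both documents, with no new scans or data. Exploratory irDCR may come out slightly less favourable.
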